2.5.1 Strategies to improve adherence to interventions

In this trial, each family has a Wechat discussion group where they can upload their biological data and contact the researcher conveniently. Researchers will check the uploaded data every

morning and give feedback to caregivers in the discussion group. When the data is not uploaded, researchers will remind the caregivers to upload data and make sure that if they have any difficulty in continuing the exercise. Researchers will also check the data uploaded automatically by the Baduanjin software to ensure the movements were adequately practiced. When unqualified exercise data is identified, the researcher will contact the caregiver to modify their exercise status and guide them to meet the requirement of exercise intensity and movement accuracy.

2.5.2 Definition of adherence

Researchers will check the uploaded data every day. If the time of exercise exceeds 30 minutes, and the maximum heart rate during the exercise is over 120 beats per minute, it is recorded as a day that meets the adherence standard. For the participants in the Baduanjin group, the score automatically rated by the Baduanjin software should also exceed 77.5. We require the participants to meet the adherence standard for at least 5 days each week. Participants that finished less than 80% required days are defined as having poor adherence.

2.5.3 Relevant concomitant care permitted or prohibited during the trial

Both groups receive standard care in the clinic during the intervention. Additional sensory integration therapy and child behavioral group or individual therapy are permitted once they complete the 3-months follow-up.

2.5.4 Provisions for post-trial care

The WeChat discussion group will be kept after the trial so that the participants can access the researchers if they have any further questions about ADHD or physical exercise.

2.6 Outcomes

2.6.1 Primary Outcome Measure:

Hyperactivity/Impulsivity score change in SNAP-IV clinician-rated scale. The Swanson, Nolan, and Pelham Questionnaire (SNAP-IV) Rating Scale is a revised version of the Swanson, Nolan, and Pelham (SNAP) Questionnaire that utilizes the DSM-IV criteria for ADHD and oppositional defiant

disorder, rated by caregivers or professionals[33,34]. It comprises three subscales: Inattention, Hyperactivity/Impulsivity, and Oppositional Defiant Disorder. The score of each item is rated with a 4-point Likert scale (0 = not at all, 3 = very much). The Chinese version of the SNAP-IV has good internal consistency ($\alpha = 0.95$) and test-retest reliability ($ICC = 0.68$), and its sensitivity and specificity for ADHD diagnosis are 0.87 and 0.79, respectively[35]. We ask the blinded clinician to rate the 9-item-Hyperactivity/Impulsivity subscale to evaluate change in ADHD Hyperactivity/Impulsivity symptoms in children. The Hyperactivity/Impulsivity subscale score is calculated by adding the 9 items; the score will range from 0 to 27. The change of score is calculated by the Hyperactivity/Impulsivity score at 3 months after enrollment (both the Baduanjin exercise group and Routine physical exercise group went through 3 months of intervention at this point) minus the Hyperactivity/Impulsivity score at baseline (enrollment).

2.6.2 Secondary Outcome Measure:

- (1) Change of Scoring evaluation of the TCM symptoms. The TCM symptom scale was developed from the guideline system for traditional Chinese medicine's new drug clinical research to evaluate the severity of TCM symptoms in children[36]. This scale includes 23 items; each presents one common TCM symptom. Each symptom is rated 1-4 points according to its severity by a trained researcher with extensive experience in TCM, using observation, auscultation and olfaction, inquiry, pulse feeling, and palpation. The total score is calculated by adding the scores of all 23 items. The change of score is calculated by TCM symptoms score after 3 months of enrollment (both the Baduanjin exercise group and Routine physical exercise group went through 3 months of intervention at this point) minus TCM symptoms score at baseline (enrollment).
- (2) SNAP-IV parent scale score change of inattention and Oppositional Defiant Disorder(ODD) subscales are used as outcome measures to evaluate the effect of treatment on inattention and ODD symptoms. Both the parent-rated and clinician-rated scores will be analyzed.
- (3) The change of Weiss Functional Impairment Rating Scale (WFIRS) scores. The WFIRS is an ADHD-specific impairment measure that is widely used across the world[37]. The items of this scale describe functional difficulties most likely to represent the patient's treatment target. This instrument has been translated into Chinese and validated in the ADHD population [38]. The scale uses a Likert scale of 0-3, and subscales including family, school, life skills, child's self-concept, social activities, and risky activities are designed to cover different areas of functional impairment.
- (4) Behavioral problems of children are evaluated by the parent version of the Achenbach Child Behavior Checklist (CBCL) and self-rated Strengths and Difficulties Questionnaire(SDQ) by the child. The CBCL scale was first published in 1976 and revised in 1983 and 1991[39,40]. It is a scale widely used internationally to assess children's behavior problems, with a three-level Likert score of 0-2 and nine subscales formed according to different ages and genders. Su et al. normalized this scale in China in 1998 and reported satisfactory psychometric characteristics [41]. The SDQ was developed by Goodman. R in 1997 and revised in 2001[42]. It is also scored by a Likert scale of 0 to 2, with 25 items divided into 5 subscales. Both parents and children over the age of 9 can use this questionnaire to report behavior problems. Du et al. have built the norm in China and reported mixed findings concerning the psychometric properties of the Chinese version of SDQ[43]. The change in scores in these rating scales will be compared between the two groups.

(5) Children's executive function is extrapolated by neuropsychological tests and ecological rating scales. The Cambridge neuropsychological test automated battery (CANTAB) is chosen to evaluate the executive function change after physical exercise. The CANTAB is a computer-based validated cognitive assessment system consisting of a battery of neuropsychological tests administered to participants using a touch screen computer[43]. This system provides accurate and sensitive computerized psychological testing. It aims to be culture and language-independent by using non-verbal stimuli in most tests suitable for school-age children and adolescents. The Motor Screening Task, Spatial Working Memory, Stop Signal Task, and Rapid Visual Information Processing are applied in this trial.

[figure not shown]
The ecological executive function of participants is assessed by the Behavior Rating Inventory of Executive Function, Second Edition (BRIEF-2). Originally developed by Gerard Gioia, this scale is an assessment of executive function behaviors at home for children and adolescents ages 5–18, mainly used to evaluate ADHD in children and has been shown to be superior to other rating systems as it taps into unique behaviors typically associated with the disorder[43]. This scale has nine different well-validated subscales and three indexes consistent with widely accepted theory: Behavior Regulation, Emotion Regulation, and Cognitive Regulation. This scale is translated into Chinese and has been proven to have convincing reliability and validity[44]. The performance change in CANTAB and BRIEF-2 will be compared between the two groups in this trial.

(6) Visual Perception of children is measured by the Developmental Test of Visual Perception-2nd edition (DTVP-2)[45]. It is a well-researched, norm-referenced measure of visual perception and visual-motor abilities in individuals ages 4 to 12. It has 8 subtests that measure different but interrelated visual-perceptual and visual-motor abilities along with 3 index scores--General Visual Perceptual Index, Motor-Reduced Visual Perception Index, and Visual-Motor Integration Index. The different visual perception performances will be tested before and after intervention and compared between groups.

(7) The sensory integration problems of children with ADHD are evaluated by Child Sensory Integration Checklist, which was first created by Xinxiang Zheng and then retested in Mainland China[46]. This scale is composed of 5 factors, including gross motor and balance, excessive tactile sensitivity and emotional instability, poor proprioception, insufficient learning ability or poor coordination, and particular problems of older children. It is assumed that physical exercise can improve the sensory integration ability of participants. Therefore, the change in the score of each factor will be compared between the two groups.

2.7 Participant timeline

Outcome measures are collected at enrolment, 3 months allocation, and 6 months post allocation. The flow of the trial is presented in Figure 1. A schematic diagram of enrolment, interventions, and assessments is described in Table 1.

TG: treatment group, CG: control group, SNAP-IV: The Swanson, Nolan, and Pelham Questionnaire

Figure 1 Flow diagram showing study design and subject allocation

Table 1 Enrolment, interventions, and assessments

| | STUDY PERIOD | | | |
|-------------|--------------|------------|-----------------|-----------|
| | Enrolment | Allocation | Post-allocation | Close-out |
| TIMEPOINT** | -2 Weeks | 0 | 3 months | 6 months |
| ENROLMENT: | | | | |

| | | | | |
|--|---|---|---|---|
| Eligibility screen | ✓ | | | |
| Informed consent | ✓ | | | |
| Allocation | | ✓ | | |
| INTERVENTIONS: | | | | |
| Baduanjin practice | ✓ | ✓ | ✓ | ✓ |
| routine physical exercise | ✓ | ✓ | ✓ | ✓ |
| ASSESSMENTS: | | | | |
| Primary Outcome: SNAP-IV clinician-rated Hyperactivity/Impulsivity score | ✓ | | ✓ | ✓ |
| Secondary Outcome: Scoring evaluation of the TCM symptoms(researcher rated) | ✓ | | ✓ | ✓ |
| Other outcome measures: | | | | |
| SNAP-IV parent/clinician-rated inattention and ODD score | ✓ | | ✓ | ✓ |
| WFIRS (parent completed) | ✓ | | ✓ | ✓ |
| CBCL (parent completed) | ✓ | | ✓ | ✓ |
| SDQ(parent and child completed) | ✓ | | ✓ | ✓ |
| CANTAB(child completed) | ✓ | | ✓ | ✓ |
| BRIEF-2 (parent completed) | ✓ | | ✓ | ✓ |
| DTVP-2(child completed) | ✓ | | ✓ | ✓ |
| Child Sensory Integration Checklist (parent completed) | ✓ | | ✓ | ✓ |

SNAP-IV: The Swanson, Nolan, and Pelham Questionnaire; TCM: Traditional Chinese Medicine; ODD: Oppositional Defiant Disorder; WFIRS: Weiss Functional Impairment Rating Scale; CBCL: Achenbach Child Behavior Checklist; SDQ: Strengths and Difficulties Questionnaire; CANTAB:

Cambridge neuropsychological test automated battery; BRIEF-2: Behavior Rating Inventory of Executive Function, Second Edition; DTVP-2: Visual Perception of children is measured by the Developmental Test of Visual Perception-2nd edition.

2.8 Sample size

Detailed information is displayed in the SAP.

2.9 Recruitment

Patients will be recruited at the child psychology clinic and TCM clinic of the Children's Hospital of Fudan University. The information of this trial will also be introduced at our 3-hour online ADHD parent training, which is provided to all the families who recently received the diagnosis of ADHD. The advertisement of this trial is also posted both in the hallway of our clinic and on our hospital's WeChat social media platform. Families interested in participating in this trial will fill in the online application form via mobile phone.

2.10 Assignment of interventions: allocation

2.10.1 Sequence generation

Recruited patients will be randomly assigned in a 1:1 ratio to the control group or the experimental group through blocked randomization. The randomization sequence is created by the center using SAS (version 9.4) with a block size of 4. An independent statistician will generate the randomization list. A sequence of subjects' IDs and intervention allocations was generated by creating a random variable and ordering that variable.

2.10.2 Concealment mechanism

The statistician will conceal the allocation sequence and place it sequentially numbered, opaque, sealed, and stapled envelopes. After signing the informed consent from parents, the study investigators will open the envelopes in consecutive orders and randomly assign the subjects to the intervention group or the control group according to the allocation scheme in the envelope.

2.10.3 Implementation

The statistical department of our hospital generates the allocation sequence. The researchers will use the prepared sealed envelopes to allocate the patient to a study arm and finish the enrollment procedures. The study group will be revealed, and intervention will be introduced after allocation to the participants.

2.11 Assignment of interventions: Blinding

2.11.1 Who will be blinded

The standard clinic care will be given by a doctor who knows that the patient is participating in this trial but is unaware of the patient's study group. The primary and secondary outcomes investigator will also be unaware of the patient's grouping. One psychiatrist blind of allocation will talk with the family about their children's ADHD and ODD symptoms and rate it with the SNAP-IV scale. Another Chinese traditional medical doctor blind of grouping will evaluate the severity of traditional Chinese medicine symptoms of children and rate it with TCM symptom scale.

All researchers conducting outcome assessments will be masked in the trial. The trial statistician will also be blinded regarding the treatment code when he develops the statistical analysis plan and writes the statistical programs, which will be validated and completed using dummy randomization codes. The actual allocation will only be provided to the study team after locking the database.

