2.4 Interventions

2.4.1 Explanation for the choice of comparators

Many cross-sectional studies support a positive relationship between routine physical activity and executive function development, decreased behavioral problems, and impulsivity control in children with ADHD. We assumed that Baduanjin exercise is superior to other routine physical exercises. Therefore, the control group is guided to take any routine physical exercise, including jogging, bike-riding, badminton, table tennis, soccer, basketball, aerobics, and rope skipping for 30 minutes, five days each week, under the supervision of caregivers. The caregivers are trained during inclusion interviews by the physician to understand the idea of aerobic physical exercise and the technique to help their child choose their favorite sports activity and make it a daily routine. Each child participating in this trial is given a Huawei fitness tracker with a heart monitor, which is used to monitor the body information during their daily exercise. Researchers will check the uploaded data of the fitness tracker on a daily basis. The time of exercise is required to exceed 30 minutes each time, and the maximum heart rate during the exercise should be over 120 beats per minute. This is the comparator of choice for the Baduanjin exercise in this study.

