2.4.2 Intervention description

The Baduanjin exercise group is asked to use the Baduanjin training system to practice the whole set of Baduanjin at least once a day and at least 5 days each week for 3 months. The Baduanjin training system is a video game designed with motion tracking and motion recognition strategy by the research team, providing a motivating full-body interactive experience for children with ADHD to engage in practice. Caregivers included in the Baduanjin intervention group were equipped with a Kinect sensor bar, connector, and software package on the day of enrolment. The software and electronic equipment installation is guided by researchers on the same day in the

hospital and at their homes later if necessary.

During the study, the children were asked to practice Baduanjin using the given software for at least 30 minutes daily, 5 times each week. They can practice any single brocade or the whole combination of 8 movements using the different game modes in the software. Instructions for movements and the variety of breath are provided in each game mode. The eight movements of Baduanjin are listed as follows:

1. Hold up the hands to regulate the triple burner;
2. Draw a bow like shooting a hawk;
3. Raise one arm to regulate the spleen and stomach;
4. Turn the head back to treat consumptive diseases and injuries;
5. Sway the head and swing the buttocks to expel the heart-fire;
6. Hold the feet by the hands to reinforce the loins and kidneys;
7. Punch with anger;
8. Hold and drop the heels to improve the health of the spine.

During their exercise, the child's motion will be captured and projected onto the screen, and their movement will be scored according to accuracy. The advice on motion adjustment is given immediately, and the feedback of data will be shown on the screen after each round of the game, then uploaded to a management website to be monitored by researchers.

The children in the Baduanjin group were asked to use the fitness tracker and uploaded data the same as the control group. The time of exercise is required to exceed 30 minutes each time, and the maximum heart rate during the exercise should be over 120 beats per minute. Researchers will also check with the data uploaded automatically by the Baduanjin software to ensure the movements are adequately practiced.

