2.12 Data collection and management

2.12.1 Plans for assessment and collection of outcomes

The outcomes will be collected at 3 months and 6 months after allocation. Considering the ongoing COVID-19 quarantine, we allow participants to finish the first outcome evaluation at 3 months \pm 4 weeks, and for the second outcome evaluation, 6 months \pm 4 weeks.

The research staff is required to receive a three-hour training session to ensure that they fully understand the protocol and standard procedures for the trial. The blinded physicians for evaluating the primary and secondary outcomes attend a one-hour training on the outcome assessment. All the research questionnaires and tests will be conducted at the Children's Hospital of Fudan University. Data will be collected with a case report form (CRF) and recorded in an ACCESS database. The description of study instruments is provided in the outcome part of this protocol. The demographic information of participants, including birth date, sex, height, weight, routine habit of exercise, and current drug use, are recorded on the CRF. The test record of CANTAB will be downloaded from the Cambridge cognition official website and automatically saved as an excel document. All data collected during the study will be kept in a locked room or protected research server. Back-ups in the study folder on this protected research server will be saved regularly (once per 3 months). Only the study team has access to these documents. To ensure this trial is applied consistently to high quality, the Clinical Trial Unit (CTU) of Children's Hospital of Fudan University will regularly monitor enrolment records, CRFs, informed consent, and data records.

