2.12.2 Plans to promote participant retention and complete follow-up

Before the beginning of the intervention, researchers and caregivers will discuss the best way to implement the exercise at home and strategies to encourage the child's participation. During the intervention, several actions were taken to engage parents and children of both groups in promoting physical exercise at home. Each family was invited to join a Wechat (a Chinese multi-purpose messaging and social media app) discussion group, where they can check their fitness tracker data with researchers daily. Children are given a set of toy coins and a money box on the day of consent signing. They can add one coin into the money box once their data are examined the next morning. Children are given a brochure containing a list of prizes and encouraged to choose gifts with values ranging from 15 to 90 coins. Gifts can be exchanged and sent to their home at any time during the intervention and within 2 months after the intervention. Furthermore, a handwritten, personally signed thank-you card from researchers is sent at the end of the first week of their intervention. Three designed medals—a bronze, a silver, and a golden- are awarded to the children at the end of each month of their intervention sequentially.

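### The blinded psychiatrist scores the primary outcome after talking with a family that knows its arm, and nothing prevents or records disclosure, so rater blinding could fail unseen

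*Protocol*

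**What the plan says.** Protocol 2.6.1 makes the primary outcome a clinician's judgement on nine items, total 0 to 27: "We ask the blinded clinician to rate the 9-item-Hyperactivity/Impulsivity subscale". Section 2.11.1 gives the only account of how that rating is made: "One psychiatrist blind of allocation will talk with the family about their children's ADHD and ODD symptoms and rate it with the SNAP-IV scale".

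The family is not blind. Section 2.10.3 states: "The study group will be revealed, and intervention will be introduced after allocation to the participants". Caregivers are then closely involved in the assigned exercise:

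- Control arm (2.4.1): the child exercises "under the supervision of caregivers".
- Baduanjin arm (2.4.2): "Caregivers included in the Baduanjin intervention group were equipped with a Kinect sensor bar, connector, and software package".
- Both arms (2.12.2): "researchers and caregivers will discuss the best way to implement the exercise at home".

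On preparing the raters, section 2.12.1 says: "The blinded physicians for evaluating the primary and secondary outcomes attend a one-hour training on the outcome assessment". Section 2.11.2 deals only with emergency unblinding and plans no procedure. SAP 3.5 repeats that the assessing physicians are blinded. The SAP variable list (section 7) has fields for adverse events, medication and reasons for stopping, but none for disclosure of the arm or for the rater's belief about it.

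**The concern.** A subjective score that rests at least partly on a conversation is only as blind as the conversation. At 3 months the family has lived with either a sensor-driven video game or an ordinary sport, and one casual remark can identify the group. The plan keeps the allocation from the rater but does not ask the family to do the same, and it would leave no trace if the arm came out. The TCM doctor's rating is exposed in the same way to the extent that it uses inquiry, one of several methods listed in 2.6.2.

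At stake is the 3-month difference in the primary outcome. If a rater who learns the arm scores one arm more favourably, even slightly, that lean enters the treatment effect. The report would have no data to show whether this happened seldom or often.

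**Working it through.** **What is in place and what is missing.** The psychiatrist is not told the arm (Protocol 2.11.1, SAP 3.5), the talk is about symptoms (2.11.1), and raters have one hour of training whose content is not described (2.12.1). Protocol sections 2.11 and 2.12, SAP 3.5 and the SAP variable list contain no request to families, no opening statement by the rater, no disclosure record and no reporting of disclosure. Table 1 (Protocol 2.7) places the baseline rating before allocation, so the exposure is confined to the 3- and 6-month ratings.

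**The plan's own figure (SAP 3.6).** Inputs: difference 3.1, SD 5.8, power 80%, two-sided alpha 0.05.

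- Normal approximation: n = 2 × [5.8 × (1.960 + 0.842) / 3.1]² = 54.95, so 55 per arm. The t-test version gives 55.93, so 56 per arm, as stated.
- Dropout: 56 / 0.95 = 58.9, so 59 per arm and 118 in total. The stated 120 fits rounding up to whole blocks of four.

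The sample size reproduces, and this point does not depend on any error in it.

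**What a rating shift would do.** Let d be the net share of ratings in which the arm is disclosed, net of any similar effect in the other arm, and s the lean in points when it is. The between-arm shift is b = d × s. With 56 per arm, SE = 5.8 × √(2/56) = 1.096, so the smallest significant difference is 1.96 × 1.096 = 2.15 points. With no true effect, the two-sided type I error is 1 − Φ(1.96 − b/SE) + Φ(−1.96 − b/SE).

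Neither d nor s is in the documents. The values below are assumptions.

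| d | s (points) | b (points) | b / 3.1 | Type I error |
|---|---|---|---|---|
| 10% | 1 | 0.10 | 3% | 5.1% |
| 10% | 2 | 0.20 | 6% | 5.4% |
| 25% | 1 | 0.25 | 8% | 5.6% |
| 25% | 2 | 0.50 | 16% | 7.4% |
| 50% | 1 | 0.50 | 16% | 7.4% |
| 50% | 2 | 1.00 | 32% | 14.9% |

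For the last row, b/SE = 1.00 / 1.096 = 0.912. The two tails are 0.1474 and 0.0020, together 0.149.

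This treats the comparison as a simple difference of two means with the planning SD. The mixed model in SAP 5.1.1 may have a somewhat different standard error.

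**The case against.** The design choice itself is sound. Families cannot be blinded to exercise, a blinded rater is the right answer, and the trial is openly labelled single-blind. Much of the rest of the case against also stands:

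- A reader might infer that rater masking is the only guard against bias. It is not. Allocation is concealed, the statistician is blinded until database lock, and the arms share the tracker, the exercise targets, the daily feedback and the rewards, which should reduce differences in expectation. Masking is the main protection against biased scoring, and that is all that is claimed.
- A reader might infer that the rating involves no observation of the child. The documents do not say so, and the TCM rating also uses observation and physical examination.
- A reader might infer that caregivers supervise the exercise in both arms. Supervision is stated only for control. In the Baduanjin arm their knowledge follows from the equipment and the home planning.
- A reader might infer that any bias must favour Baduanjin. That is plausible, since the protocol assumes its superiority and the research team designed the game, but the documents hold no data on expectation, and control children choose a favourite sport.
- The interview is already confined to ADHD and ODD symptoms, and the training may cover disclosure. Confining the topic does not stop a family from volunteering the exercise, and the text does not say what the training covers.

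The objection to testing the blind by guesses or exclusions is also right. A guess made after scoring may reflect improvement the rater has seen, and dropping disclosed ratings selects on an event after randomisation. The fix treats both accordingly.

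**Conclusion.** The point holds as a cheap, worthwhile improvement. The rater talks with an informed family, the arms are easy to tell apart in conversation, and the plan neither discourages disclosure nor records it. A reader might go further and conclude that the blind was broken or the primary result biased. The documents show only that this could happen without being noticed.

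The size is unknown. On the assumed ranges it runs from negligible (0.1 point, type I error 5.1%) to serious (1.0 point, 14.9%), and the plan collects nothing that would tell the two apart. No change to the sample size or the primary analysis follows.

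**What to change.** In Protocol 2.11.1 and 2.12.1, with matching entries in the SAP:

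- (a) Before the 3- and 6-month ratings, existing staff other than the rater ask child and caregiver not to mention the type of exercise, the equipment or the group. The rater opens with the same request. Do the same for the TCM rating.
- (b) The rater records on the CRF whether the arm was disclosed. The SAP adds the field to its variable list and reports disclosure by arm.
- (c) Any guess of the arm, or any analysis without disclosed ratings, is descriptive only. It carries the caveat that it conditions on a post-randomisation event and does not replace the primary analysis.
- (d) Describe the primary outcome as blinded-rater, unblinded-informant. Steps (a) to (c) cannot remove the family's own expectations, so the description should be plain about them.

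Protocol 1.3 planned conduct to March 2022 and SAP 2.0 is dated October 2022, so the visits may be over. If they are, apply (d) and state that rater blinding was not tested.

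The cost is two small additions at existing visits and a few lines of reporting, with no extra staff. The downside is that disclosure, if frequent, has to be reported.
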